Do probiotics modulate the intestinal microbiome in extremely premature infants?

Principle Investigator: [name]

REB16-0542

October 11, 2017

Project Title: Do probiotics modulate the intestinal microbiome in extremely premature infants?

Project Type: Primary – Research
Secondary – Clinical care

Principal Applicant (PA): [name] (Concept, literature review, study design, drafting application)
Co-Principal Applicant: [name] (Concept, study design and statistics, drafting application)

Collaborators: [name] (Microbiome Research Scientist)
[name] (ACHRI - Sample analysis)
[name] (MSc student in Microbiology)
[name] (Infection prevention and control)
[name] (Epidemiology and data analysis)
[name] (ACH/FMC pharmacists: product management)

Project Summary:

The gut microbiome plays a significant role in balancing the inflammatory system in the immature gut. A breakdown in this balance with altered colonization of the microbiota in very low birth weight (VLBW) preterm infants is associated with increased feeding intolerance, NEC and sepsis. Probiotics are proposed to normalize microbial populations and decrease intestinal disease in preterm infants. There is limited data linking clinical outcomes with the biology of probiotics. We aim to study the colonization of the GI tract with probiotic species contained in a specific probiotic blend – Florababy – in VLBW preterm infants.

Stool microbiome will be analyzed at 4 time points in 2 groups (one given Florababy and the other no) of infants less than 1000g birth weight and < 29 weeks gestation. A comparison of stool microbiome analysis and the incidence of feeding intolerance and time to reach full feeds in the two groups will be made.

1. What you want to do.

Research question

Does Florababy change the gut colonization pattern in a measurable way in a population of very premature neonates?

Hypothesis:

Florababy probiotics can multiply in the gut and change the colonization pattern of the premature intestinal tract in a measurable way.

Primary outcome: difference in stool microbiome after 4 weeks of Florababy or compared to infants who didn't receive Florababy.

Secondary outcomes: i) difference in stool microbiome 1week after the study drug administration is stopped.

ii) incidence of feeding intolerance and time to reach full feeds.

3. Why this is important.

At a glance:

- a) Probiotics are proposed as universal supplements in preterm neonates. Results of probiotic administration in neonates are conflicting.
- b) There is very little data linking clinical outcomes with the biology of probiotics. Gaps in current knowledge are the ecology of probiotics, their fate after administration of a specific product to a given infant, and the degree of influence on the pre-existing and/or developing microbiome.
- c) It is essential that biological and mechanistic data are obtained and correlated with clinical data for a given probiotic.

2.1 Microbiome and the neonate.

There is growing recognition of the importance of the relationship between the human body and the microbial flora that coexist within it. The “human” body contains over 10 times more microbial cells than human cells, carrying 150 times as many genes as the human genome. The “microbiome” describes the collective genomes of these microorganisms. Microbial populations residing in the GI tract are the largest and most complex microbiome in our body. Studies of the intestinal microbiome have revealed a wide and variable microbial population whose composition is affected by host factors such as genetics, the immune system and environmental factors. The microbiome has a myriad of roles locally and systemically. There has been an explosion of information about its effects on local and systemic immunity and inflammation, the nervous system, the endocrine environment and metabolic states, etc. with several reviews that have been published recently (1-5).

The fetal intestine was initially thought to be sterile. However, recent studies suggest that it may be exposed to microbes via the amniotic fluid (6-8). During and after birth, microorganisms from the maternal vagina and intestine, from the maternal skin surface, from maternal breastmilk and oral cavity, and from the environment colonize the neonatal GI tract. Many factors have been shown to alter the gut flora in neonates such as gestational age and feeding patterns. Data on the development of the normal microbiome in well term infants is still limited. It shows a very complex process where waves of microbial species get established in a careful orchestrated order with multiple interactions between them and the host (9-14). Many details of this process remain unknown.

Furthermore, the intestinal microbiomes of infants admitted to NICUs have different patterns compared to infants not admitted to NICUs. This is due to exposure to a different environment in NICUs, and the use of antibiotics and sterile formulas. There is even less data about the establishment of the microbiome in very preterm infants, how that evolves with time, what constitutes a “good” profile and how it correlates with intestinal or systemic pathology. What we know shows that the microbiome in preterm infants demonstrates decreased diversity, altered species proportions and even different behavior of the same species when compared with the term infant (15-17).

2.2 Microbiome and intestinal disease in the neonate.

The microbiome plays an essential role in nutrition, mucosal immunity, and GI epithelial integrity. Current evidence suggests that interactions between the altered microbiome and the intestinal epithelium play an important role in the development of feeding intolerance, allergy, sepsis and necrotizing enterocolitis (NEC) (18-20).

NEC is a multifactorial disease and one of the major pathologies affecting preterm infants. It is associated with significant mortality and morbidity, including long term neurologic disability. Systematic interventions to predict and prevent NEC have generally remained elusive. Feeding breastmilk and colostrum to preterm infants is helpful and use of probiotics has shown good results in a number of studies, though significant concerns remain. Concerns include: the limited safety data for infants born < 1000g and a domestically available probiotic formulation with demonstrated efficacy, safety, and regulatory approval. There remain concerns that the regulatory framework for approval of probiotics does not approach the rigor for drugs (21-22). Systematic reviews of randomized controlled trials concluded that probiotics as a group significantly reduce the incidence of severe NEC (23). The principle and methodology of such generalizations is controversial (24-26). Better tools are needed to aid in the understanding and monitoring of probiotic administration.

The technology available to define the intestinal microbiome has been a sizable obstacle. The vast majority of species cannot be cultured and the genomic technologies have just only very recently reached a level where the ratio of cost and resolution allows for reasonably efficient research use.

2.3 Techniques to study gut microbiota and microbiome.

The composition of the gut microbiota has been classically analyzed using differential media to distinguish between populations of bacteria based on their metabolic requirements. The capability of these culture-based techniques to discriminate between different bacterial phylogenetic groups is limited. It is estimated that 80% of the gut microbiota cannot be cultured using these techniques. Recent reviews emphasized the role of genomic technology in mapping the microbiome, providing an unprecedented amount of detail on the constituent species (27-29). These genomic techniques are capable of identifying commercial probiotic strains. One of the leading techniques employed currently is 16S rDNA amplification and sequencing. It is available in Calgary through the Genomics facility at Alberta Children’s Hospital Research Institute (ACHRI).

3.1 Probiotic administration results in preterm infants

The subject of probiotic administration to preterm infants is important. There are at least 20 meta-analyses and systematic reviews identified with a Pubmed search. This is a large number despite only 24 trials in the latest Cochrane review and a meta-analysis from April 2014 (23). It is also important to note the contradictory statements in that review. It begins by stating: “Based on the available evidence for probiotics efficacy and safety in preterm infants, the number of infants enrolled, the narrow confidence intervals, and the probiotics safety profile, a change in practice is warranted at this stage. More studies to address the optimal preparation, dosing, and duration of therapy are still needed in head to head comparative studies rather than placebo controlled trials.” Immediately followed by: “Although all included trials evaluated probiotics use in preterm infants, the trials were highly variable with regard to enrolment criteria (that is birth weight and gestational age), baseline risk of NEC in the control groups, timing, dose, formulation of probiotic used, and feeding regimens.(23)The validity of our review’s results is potentially compromised as it included trials that utilized different preparations and dosing regimens of the intervention under study; and data on the highest risk population (ELBW infants) could not be retrieved.”

Two sizeable recent studies were published or had outcome data released after the Cochrane review. The recent Probiotics in Preterm babies Study (PiPS) was done in Britain and enrolled 1315 infants of 30 weeks gestational age or less. It used a single bacterial strain – *Bifidobacterium breve*. This study did not find any significant clinical impact of that particular probiotic and the findings do not support the use of *Bifidobacterium breve* for the prevention of NEC (30). Another recent RCT studied *Lactobacillus Reuteri* in 400 VLBW infants of less than 32 weeks gestation and it concluded that there was no effect on NEC

or NEC and mortality though late onset sepsis was significantly reduced (31). The combined size of these 2 studies is large, over 1/3rd of all previous RCTs' population in the 2014 Cochrane review.

3.2 Florababy.

Florababy is a 5 strain proprietary probiotic blend produced by Renew Life Canada. It contains 4 billion total CFU of 4 *Bifidobacterium* species (*Breve, bifidum, infantis and longum*) together with *Lactobacillus rhamnosus*. The non-medicinal ingredients are maltodextrin and ascorbic acid. Florababy has been used for only a few years in neonates in Canada. A recently published retrospective cohort study compared data from 17 months before and after introduction of Florababy in a level III NICU for all infants less than 32 weeks gestational age at birth (32). It showed a positive impact on NEC stage 2 or more from a baseline of 10% in infants less than 32 weeks, double the current rate in Calgary. The amount of breastmilk feeding in that cohort is not specified. There was no impact on health care associated infections.

3.3 Biology of probiotics and relation with effects – gaps in knowledge.

The above underscores the need for specific product trials in this population as well as the pressing need for markers and biological understanding. A lot of the limited data concerning the fate of probiotics in preterm infants may not be applicable to current NICU care and feeding practices or was generated before latest genomics technology was available (33-43). The percentage of infants and interval of time in which specific probiotic strains are established in the gut, any differences between strains, differences within a population fed fresh breastmilk and correlation with clinical effects including tolerance of enteral feeds and time to reach full feeds are very important aspects. They need to be clarified for contemporary practices, with best methods, in order to assess and optimize the use of probiotics in the neonate. Using meta-analysis to advocate for an intervention when the biological pathways were not clear has been a source of error before in medicine (44).

3.4 Definition of Feeding Intolerance.

Feeding intolerance will be defined as the inability to digest enteral feedings associated with: i) gastric residual volumes of more than 50% of the volume of the previous feed, ii) abdominal distention and/or emesis, iii) disruption of the baby's feeding plan (decrease, delay or discontinuation of enteral feedings).

4. How you are going to do it.

4.1 Study design

This study will occur in a randomized controlled trial setup in the Calgary NICUs. Florababy probiotic will be administered to infants in the drug arm and clinical outcomes and gut microbiome data will be compared between the two groups. The projected starting time is Oct 2017. Study duration will be 18 months.

4.2 Study Population

Premature infants born less than 29 weeks gestation and < 1000g birth weight admitted to the NICU at Foothills Medical Centre in Calgary.

a) Inclusion Criteria: Preterm infants born at less than 29 weeks gestation and < 1000g birth weight.

b) Exclusion Criteria: Infants with major congenital anomalies, hypoxic-ischemic injury and NEC or bowel perforation before 72 hours of life.

4.3 Sample Size and feasibility

A total of 100 infants of birth weight <1000g are born annually and admitted to FMC NICU.

Assuming that 80% of parents' consent to their infant's participation in the study, it will be feasible to complete enrollment of 60 babies in the first year of the study. This study will randomize 30 infants to be given probiotics and 30 infants be in the control group where no probiotic given. The 2 groups will be matched by gender, gestational age +/- one week, birth weight +/- 100g, SGA vs AGA/LGA status and type of delivery.

A sample size of 30 infants per group will allow for a power of 0.8 and an alpha of 0.05 for a two-tailed Wilcoxon-Mann-Whitney test to detect a 0.7 effect size when comparing relative abundance of stool probiotic microbial species in the group given Florababy versus the one given placebo, conservatively assuming a background logistic distribution (G-Power 3.1 software).

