4.4 Variables collected

- a) Demographic variables: Gestational age, birth weight, head circumference at birth, gender, mode of delivery, singleton/multiple and rank, maternal administration of corticosteroids and antibiotics.
- b) Clinical variables: Apgar scores, umbilical cord pH and base excess, first patient blood gas pH and lactate, day of life at start of feeds and at start of study, total days of study drug, antibiotic use during NICU, use of inotropes and vasoactive substances, steroids and medical and/or surgical treatment for PDA, type of feeds during NICU and at discharge.

- c) Outcome variables: mortality; total days of TPN, total days NPO and number of separate NPO events; age, head circumference and weight at discharge home; diagnosis of: feeding intolerance, time taken to reach full enteral feeds (at least 150ml/kg/day), suspected NEC, NEC, cow milk protein allergy, late onset sepsis, BPD, ROP.

4.5 Study protocol.

Infants will be identified within 24 hours of birth and parents will be approached for informed consent.

Once consent is obtained, subjects will be randomly assigned in blocks of 4 to receive either Florababy probiotics orno. Investigators will conduct the randomization using a computer-generated table of random numbers generated at the University of Calgary.

Preparation and Administration of Study Drug

The study probiotic will be started after the first stool sample is obtained and after informed parental consent. Very small amounts of breast milk/colostrum (0.1ml to 0.2ml every 4 hours) are usually given to all premature babies within the first 48 hours of life. Actual feeds of breast and/or human milk (donor milk) are initiated from 72 hours onwards (starting at 10ml/kg/day and increasing slowly thereafter). The study probiotic (at a dose of 0.5g per day) will be started at or after 72 hours of life. It will be administered in 1 ml of sterile water prior to a feed.. No drug will be given to infants in the control group. If the infant is placed NPO, the study drug will be stopped and restarted together with refeeding.

The study probiotic will be given until 34 weeks corrected gestational age.

Sample collection

Nurses will collect the stool samples at 4 time points: prior to, two weeks and four weeks after probiotic administration is commenced, and one week after it is stopped. Stool samples for the control group will be done at a matched feeding and gestational age time points.

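### The rank test of probiotic abundance that sizes the trial appears in no analysis plan, and no listed analysis is named as primary

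*Protocol*

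**What the plan says.** **Primary outcome (protocol, section 1).** It reads "Primary outcome: difference in stool microbiome after 4 weeks of Florababy", compared with infants not given the product. No metric or test follows. The post-treatment stool is secondary: "difference in stool microbiome 1week after the study drug administration is stopped".

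**Aim and question.** The Project Summary says "We aim to study the colonization of the GI tract with probiotic species contained in a specific probiotic blend". The research question is wider: "Does Florababy change the gut colonization pattern in a measurable way".

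**Sample size (protocol 4.3).** "This study will randomize 30 infants to be given probiotics and 30 infants" to no probiotic. The justification is power 0.8 at alpha 0.05 for a "two-tailed Wilcoxon-Mann-Whitney test to detect a 0.7 effect size when comparing relative abundance of stool probiotic microbial species", with a logistic parent distribution.

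**Analysis (protocol 4.6, Bioinformatic analysis, and the SAP).** The two texts give the same three microbiome analyses:

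- a two-sided Mann-Whitney test on the Shannon index, with FDR correction;
- PERMANOVA on the weighted UniFrac distance matrix;
- DESeq2 negative binomial models for individual OTUs.

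The SAP's only other tests, t and chi-square, are for characteristics variables. Neither text labels an analysis primary or ties one to week 4, although protocol 4.5 schedules four stools per infant.

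**The concern.** A sample size statement makes a promise about a particular test on a particular variable. Here that test is absent from the analysis plan, so the stated power supports nothing the plan commits to doing.

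The primary outcome does not close the gap. It fixes when the difference is assessed but not what counts as a difference. Three analyses could each be said to answer it, and they measure different things: diversity within a stool, distance between whole communities, and abundance of single OTUs. If they disagree, for example with Shannon null and one OTU significant, the trial could be reported as positive or negative, and no written rule says which. That choice would be made with the results in view and could not be repaired afterwards.

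**Working it through.** **1. Match the sizing test against the listed analyses.**

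| Place | Variable | Test | Called primary? |
|---|---|---|---|
| Protocol 4.3 | Relative abundance of probiotic species | Wilcoxon-Mann-Whitney, two-sided 0.05 | No, but sets n |
| Protocol 4.6 and SAP | Shannon index | Mann-Whitney with FDR | No |
| Protocol 4.6 and SAP | Weighted UniFrac distance | PERMANOVA | No |
| Protocol 4.6 and SAP | Count of each OTU | Negative binomial model (DESeq2) | No |

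The second row shares a test with the first but not a variable. The fourth is closest in variable but uses another test, one OTU at a time. No row matches the first.

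**2. Reproduce the 4.3 figure.** Inputs from 4.3: n = 30 per arm, effect d = 0.7, two-sided alpha 0.05, logistic parent. Using the asymptotic relative efficiency (ARE) method:

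- ARE (logistic) = π²/9 = 1.097
- effective n = 30 × 1.097 = 32.9 per arm
- noncentrality = d × √(effective n / 2) = 0.7 × √16.45 = 2.84
- degrees of freedom = 2 × 32.9 − 2 = 63.8; critical t = 2.00
- power from the noncentral t = **0.798**

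The stated 0.8 reproduces. A simulation of the rank test on logistic data (20,000 runs) gives 0.78. The figure depends on the logistic parent: with a normal parent (ARE 0.955) it is 0.740.

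**3. Can the 0.8 be carried over?** For PERMANOVA and DESeq2 the documents give no effect size or variance, so power cannot be computed. For Shannon the same formula applies, but the effect has to be assumed. With 30 per arm, logistic parent, before FDR correction:

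| Assumed Shannon effect | 0.4 | 0.5 | 0.6 | 0.7 | 0.8 | 0.9 |
|---|---|---|---|---|---|---|
| Power | 0.36 | 0.51 | 0.67 | 0.80 | 0.89 | 0.95 |

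The 0.8 carries over only if the Shannon effect is also 0.7 and FDR correction costs nothing. The documents support neither condition.

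**4. Cost of leaving three analyses unranked.** As an illustration, treat them as three independent tests at 0.05. The chance of at least one false positive is 1 − 0.95³ = 0.143. Independence is an assumption, and the true figure depends on how the analyses correlate.

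**5. What the 4.3 test itself requires.** The 30 per arm are infants randomised, with no allowance for a missing week-4 stool. Mortality is among the recorded outcomes ("Outcome variables: mortality; total days of TPN"), but no rate is given, so the losses below are assumptions.

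| Week-4 stools per arm | Power at d = 0.7 | Effect detectable with power 0.8 |
|---|---|---|
| 30 | 0.80 | 0.70 |
| 27 (10% lost) | 0.75 | 0.74 |
| 24 (20% lost) | 0.70 | 0.79 |

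**The case against.** The best defence is that the documents, read together, imply the primary comparison. Section 4.3 gives variable, test, sidedness and alpha; the aim concerns colonization with the product's species; and the hypothesis speaks of the probiotics multiplying in the gut. On that view the test was merely left out of the analysis text. DESeq2 would also compare OTUs from the probiotic taxa between arms, so the question is not ignored. And this is a 60-infant mechanistic study meant to generate further hypotheses.

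The inference about intent is reasonable, and it is why the 4.3 test is the natural choice of primary. It does not settle the matter. The research question and the second half of the hypothesis refer to the colonization pattern as a whole, which fits the three listed analyses equally well, and the SAP is the document the analyst will follow. DESeq2 is a different test, to which the 0.8 does not transfer. A study that declares a primary outcome, an alpha and a power needs a named test, whatever its size.

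Three smaller objections have some force:

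- The primary outcome refers to four weeks of product, while protocol 4.5 counts four weeks from the start of administration, and these differ for an infant whose administration was interrupted. Only one scheduled stool fits either reading, but the SAP should identify it explicitly.
- Section 4.3 does not say that the species are summed. Summing is a choice made to keep a single test at 0.05. "Florababy is a 5 strain proprietary probiotic blend", and testing five species separately at 0.05/5 = 0.01 would bring power at d = 0.7 down to about 0.58.
- The Shannon series and the loss figures rest on assumed inputs. They show how far the 0.8 can move and do not estimate the trial's actual power.

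**Conclusion.** The concern holds and should be fixed before analysis. The test that justifies 30 per arm is in neither the SAP nor the protocol's analysis section, and none of the three listed microbiome analyses is designated primary. The time point is set at 4 weeks; the deciding metric is not.

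The sample size arithmetic is correct on its stated logistic basis. What fails is the link between it and the plan: the 0.8 describes an analysis that would not be run, and the power of those that would be run is unknown from the documents. This conclusion rests on comparing the texts and needs none of the assumed effects or losses.

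**What to change.** **Preferred.** In the SAP and in the primary outcome, name one primary analysis that matches 4.3: the two-sided Wilcoxon-Mann-Whitney test at 0.05 on a single summed relative abundance of the Florababy taxa in the week-4 stool (for controls, the matched time point of protocol 4.5), one sample per infant, compared by randomised arm. In addition:

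- fix the taxon list, or the taxonomic level, with the laboratory before analysis;
- label Shannon, PERMANOVA, DESeq2 and the two-week stool as secondary or supportive (the post-treatment stool is already secondary), and give the qPCR panel of protocol 4.6 a rank as well;
- state that power 0.8 assumes a logistic parent and a week-4 stool from all 60 infants, and say how infants without one are handled.

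**Alternative.** If the broader question is meant to be primary, name one of the three listed analyses at week 4 and restate the effect size and power for it.

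**Cost.** The preferred route takes one SAP paragraph, a reworded outcome and an agreed taxon list, with no new infants, samples or sequencing. Its drawback is a narrower primary question: Shannon, PERMANOVA or DESeq2 alone could no longer carry the primary claim. The alternative keeps the wider question but needs a new power justification, which might not support 30 per arm.
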